Cue-elicited craving. Human studies of the effects of 5-HT2C agonists on cue-elicited drug craving have not been reported. To address this objective, we will utilize an established cue reactivity task to assess peak provoked craving (PPC). This procedure, which involves assessing craving during a cue exposure task (lighting a cigarette and attending to cues) while in a period of short-term abstinence, has been demonstrated to reliably induce acute craving [71]. Given the potential for differential medication effects on tonic vs. phasic craving [74], tonic craving will also be assessed as a component of the repeated self-report assessments (noted below).

Simulated lapse. The cue reactivity task will lead directly into the simulated lapse procedure developed by [name], who is a consultant on this project [38, 75]. Importantly, preclinical evidence shows that lorcaserin reduces both nicotine reinstatement and self-administration. The [name] paradigm is the only validated laboratory procedure that models each of these outcomes [38]. In this procedure, a nicotine deprivation period (e.g., overnight abstinence) provides a context to study medication effects on reinstatement [38]. Participants will be presented with a package of their preferred cigarettes (participants will be asked to bring one unopened pack in to the session). Participants will given the choice to initiate cigarette smoking, or to delay smoking for up to 50 minutes in exchange for monetary reinforcement. Prior studies show that a reinforcement schedule of \$1 for every 5 minutes results in participants resisting, on average, for 25 minutes, providing ideal variability in time to reinstatement [38]. If no lapse occurs (i.e., the participant resists for 50 minutes), participants will not be forced to smoke a cigarette. Following the initial decision to smoke, participants will complete assessments of craving, withdrawal, and subjective effects (described below).

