Next, a 60-minute period of ad libitum smoking will ensue [68]. Participants will be presented with a tray containing 8 cigarettes from the package, and will have the opportunity to smoke additional cigarettes at their discretion [68]. Again, participants will not be forced to smoke a cigarette. Repeated ratings of craving, withdrawal, and subjective effects will be taken at 15-minute intervals during the self-administration period. A follow-up measure of expired CO will be taken at the end of the session to measure CO "boost", an additional index of cigarette intake.

The primary outcomes for the human laboratory sessions consist of 1) nicotine reinstatement (i.e., minutes of resistance to smoking reinstatement), and 2) nicotine self-administration (i.e., cigarettes consumed during ad libitum smoking). These primary outcomes are selected because they reflect objectively defined behaviors analogous to those reported in preclinical studies of 5-HT2C medications. Secondary human laboratory outcomes will include peak-provoked craving during the cue exposure task, CO boost, and subjective effects during nicotine self-administration, e.g., assessed by the **Modified Cigarette Evaluation Scale** [90] and the **Drug Effects Questionnaire** [91]. The **Positive and Negative Affect Scale** [92] will also assess change in mood.

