	Locator form	10
	AUDIT	2
	TLFB (since last visit)	10
	NDSS	3
	WISDM	10
	Yale Craving Scale	5
	TQSU	1
	UPPS-P	5
	Contemplation Ladder	1
	Three Factor Eating Questionnaire	3
	Reward-Based Eating Drive Scale	2
	Simplified Nutritional Appetite Questionnaire	2
	PROMIS Depression/BDI-II	4
	Cigarette Self-efficacy Questionnaire	1
	Stop signal	10
	CPT	10
	Reward Responsiveness Test	15
	Monetary Choice Questionnaire	2
	Cigarette Discounting Task	2
	Food Discounting Task	4
	Cigarette Purchase Task	2
	SAFTEE/Adverse Effects Checklist	10
Between Baseline & Follow	Call participant on days 2 and 4 to assess side effects	10
up visit 1	SAFTEE/Adverse Effects Checklist	10
Follow up visit 1 (including	Expired CO/Breath Alcohol	4
smoking session)	Weight	2
omoning coccien,	Blood draw	5
	Take dose of medication	2
	Pill count	2
	PROMIS Depression/BDI-II	4
	Cigarette Self-efficacy Questionnaire	1
	Cigarette Purchase Task	2
	Cigarette Discounting Task	2
	Monetary Choice Questionnaire	2
	Stop Signal task	10
	CPT	10
	Food discounting task	4
	Yale Craving Scale	5
	Reward Responsiveness Test	15
	PANAS	2
	Heart rate/blood pressure	5
	Three Factor Eating Questionnaire	3
	Reward-Based Eating Drive Scale	2
	Simplified Nutritional Appetite Questionnaire	2
	SAFTEE questionnaire	8
	Adverse Effects Checklist	5
	Cue elicited craving	10

VISIT	MEASURE/PROCEDURE	TIME (MINS)
	Simulated lapse paradigm	120
	Drug Effects Questionnaire	2
	Modified CEQ	5
Washout	7 days with no medication	
	Weight/Blood Pressure	5
	TLFB (since last visit)	5
	SAFTEE/Adverse Effects Checklist	2
	Simplified Nutritional Appetite Questionnaire	2
	Dispense 2 nd medication	10
Follow up visit 2 (including	Expired CO/Breath Alcohol	4
smoking session)	Weight	2
	Blood draw	5
	Take dose of medication	2
	Pill count	2
	PROMIS Depression/BDI-II	4
	Cigarette Self-efficacy Questionnaire	1
	Cigarette Purchase Task	2
	Cigarette Discounting Task	2
	Monetary Choice Questionnaire	2
	Stop Signal task	10
	CPT	10
	Food discounting task	4
	Yale Craving Scale	5
	Reward Responsiveness Test	15
	PANAS	2
	Heart rate/blood pressure	5
	Three Factor Eating Questionnaire	3
	Reward-Based Eating Drive Scale	2
	Simplified Nutritional Appetite Questionnaire	2
	SAFTEE questionnaire	8
	Adverse Effects Checklist	5
	Cue elicited craving	10
	Simulated lapse paradigm	120
	Drug Effects Questionnaire	2
	Modified CEQ	5

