## II. Data Analysis/Statistical Considerations

Primary and secondary outcomes will be evaluated using mixed linear effects models with condition (lorcaserin, placebo) as a within-subjects factor and medication order as a between-subjects factor. Maximum likelihood estimation will be used to account for missing data by analyzing all available cases. The primary outcomes are 1) minutes of resistance to smoking reinstatement and 2) number of half cigarettes smoked during the ad lib session. Using the same model, we will also examine secondary outcomes including: impulsive choice (k value from monetary discounting task and cigarette discounting task), impulsive action (commission errors on CPT), and reward response bias as measured by the Reward Responsiveness Test.

Statistical Power. To achieve adequate power (.80) to detect medium effects of medication on our primary outcomes, we will recruit a sample of 42 smokers in order to arrive at a final sample of 34 (allowing for up to 20% attrition). Given no prior data on lorcaserin's effects on laboratory outcomes, we reviewed effects reported in similar screening studies with other medications. In a study using the lapse paradigm proposed here, varenicline had a medium to-large effect on duration to reinstatement (Cohen's d = .72) and a large effect for self-administration (d = 1.5). To account for the possibility of stronger effects for varenicline relative to lorcaserin, our power analyses assumed a medium effect size. We assumed a within-subjects correlation of 0.60 for laboratory outcomes (as reported in prior human laboratory screening studies) and an alpha level of .05. We estimated power in G\*Power software using a fixed effects, within-subjects design and two time-points. Conservatively, a sample of N = 34 allows sufficient power (.80) to detect a medium effect on the primary outcomes (Specific Aims 1 and 2). Although human data are not available to inform the predicted effect size for Aim 2, preclinical studies using this medication, and an analogous behavioral task, suggest large effects of medication. For our supplementary aim (evaluating indirect effects on the primary outcomes via impulsivity and craving), simulation studies indicate that the proposed analysis, utilizing a bootstrap procedure, will provide sufficient power (.80), given the planned sample size, to detect mediated effects in medium-to-large effect size range.

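### Does stating the self-administration outcome in both cigarettes and half cigarettes, without detailed counting rules, put the second primary analysis at risk?

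*Combined protocol and SAP*

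**What the plan says.** Under V. Data Collection Procedures, the text on Follow-up Sessions 1 and 2 names two primary outcomes: minutes of resistance, and "nicotine self-administration (i.e., cigarettes consumed during ad libitum smoking"). II. Data Analysis/Statistical Considerations keeps the first and gives the second as "number of half cigarettes smoked during the ad lib session".

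The session runs in this order. The participant may smoke, or may delay for up to 50 minutes for payment. For those who smoke: "Following the initial decision to smoke, participants will complete assessments of craving, withdrawal, and subjective effects (described below"). For those who do not: "If no lapse occurs (i.e., the participant resists for 50 minutes), participants will not be forced to smoke a cigarette". The ad lib phase follows: "Next, a 60-minute period of ad libitum smoking will ensue". The supply is then described: "Participants will be presented with a tray containing 8 cigarettes from the package, and will have the opportunity to smoke additional cigarettes at their discretion". Table 1 allots 120 minutes to the "Simulated lapse paradigm".

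**The concern.** This is one of only two primary outcomes, and four things about it are not written down:

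- which unit is used;
- how a partly smoked cigarette is scored;
- whether a cigarette smoked at lapse is counted;
- whether the hour starts at lapse or at minute 50.

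Two analysts could therefore derive different values from the same session.

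The lapse cigarette looks the most serious of these. If the count covers only the ad lib hour, a full resister's first cigarette falls inside it and a lapser's falls before it. A drug that makes more people resist for all 50 minutes could then appear to do less for self-administration than it does.

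**Working it through.** **Inputs.** From the analysis section: N = 34 analysed, correlation 0.60, alpha .05, a medium effect (no number is given; read here as d = 0.5) and target power .80. The documents give no standard deviation for cigarettes smoked and no share of full resisters. Every SD and share below is an assumption.

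**1. The plan's own figure.** For two sessions per person, dz = d / √(2(1 − r)) = 0.5 / √0.8 = 0.559. The noncentral t with 33 degrees of freedom, two-sided, gives power .886. Power .80 would need N = 28. The plan's N = 34 at .80 corresponds to dz = 0.50 (power .808). The stated sample is therefore conservative, as the plan says.

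**2. Unit.** Half cigarettes = 2 × cigarettes. The mean difference and the SD both double, so dz = (2 × 0.5) / (2 × √0.8) = 0.559 and power is again .886.

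**3. Partly smoked cigarettes.** Rounding to a step h adds about h²/12 to each session's variance, so dz = 0.5·SD / √(0.8·SD² + 2h²/12).

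| Assumed SD (cigarettes) | Power, nearest half (h = 0.5) | Power, nearest whole (h = 1) |
|---|---|---|
| 1 | .870 | .821 |
| 1.5 | .878 | .857 |
| 2 | .882 | .870 |

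At an assumed SD of 0.75 and mean of 2, simulation gave .853 for nearest half, .779 for nearest whole, .774 for every cigarette lit and .763 for finished cigarettes only. The widest gap is .853 − .763 = .09. It separates the resolution implied by the analysis section from a rule that appears nowhere in the plan.

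**4. Cigarette smoked at lapse.** Suppose a net k of 34 participants resist fully on lorcaserin only, c cigarettes are smoked at lapse, and total intake is the same for lapsers and resisters. The ad lib difference then shrinks by k·c/34. For k = 5 and c = 1 that is 5/34 = 0.147 cigarette. At SD 1, d becomes 0.5 − 0.147 = 0.353 and power .608. At SD 2, d becomes 0.426 and power .770. For k = 1 and c = 1 the shift is 0.029 and power is .846 to .867.

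This subtraction treats 0.5 as an effect that exists before the shift. The plan assumes a medium effect on the primary outcome, which is the ad lib count. On that reading nothing is subtracted and power stays at .886.

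**5. Start of the hour.** The written order is decision, ratings, then the ad lib period. A start tied to the lapse fits: lapse at the cited average of 25 minutes gives 25 + 60 = 85 minutes, and full resistance gives 50 + 60 = 110, both within Table 1's 120. No passage mentions a fixed minute-50 start. The 25 undescribed minutes (50 − 25) appear only if one is supposed.

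**6. Value of adding a total count.** With an assumed mean of 2, SD 1 and independent lapse indicators, adding one lapse cigarette when 90% lapse in both conditions leaves the difference at 0.48 and lowers power from .859 to .789. With 80% lapsing on placebo and 60% on lorcaserin, the difference rises from 0.48 to 0.68 and power from .860 to .942. That rise of 0.20 is the effect on resisting, which the first primary outcome already measures.

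**The case for a change.** The strongest case for a change is that a primary outcome should be derivable in one way only, and that a few sentences would secure this. Three parts of that case stand. The two sections do use different units, and the procedures section, with its tray of 8, never mentions halves. No scoring rule is given for a partly smoked cigarette. And nothing says that the amount smoked at lapse is recorded, or states outright when the hour starts for someone who resists for all 50 minutes.

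The rest is weaker. Both definitions restrict the count to the ad lib phase, and the wording on the tray treats those cigarettes as further ones, so a plain reading excludes the lapse cigarette. The power range of .608 to .770 needs a net 5 of 34 full resisters, an assumed SD and equal total intake together. Nor is k/34 a true ceiling, because it presumes at most one cigarette before the counted hour. The plan's own precedent also points away from serious masking: it reports that varenicline, in the same lapse paradigm, had d = .72 on time to reinstatement and 1.5 on self-administration.

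**Conclusion.** No change follows. The unit mismatch is a clerical inconsistency with no effect on inference. The missing scoring detail is a gap that analysts would fill sensibly by counting to the half cigarette, as the analysis section indicates. The same rule would apply to both sessions of a double-blind crossover in which each participant is their own control. At assumed SDs of 1 to 2 cigarettes the cost is at most .886 − .870 = .016 in power, which leaves it above the planned .80.

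A total count over both phases would be an optional extra. It mixes the first primary outcome into the second and adds little to what is already collected: resistance times show who held out for 50 minutes, and the end-of-session CO reading follows both smoking phases.

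This conclusion rests on reading the medium effect as d = 0.5 on the ad lib count, on scoring to halves, and on taking the session order as written. If the team settles the unit, the rounding convention and the start time in its scoring notes, the planned analysis stays the same.

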# **Exclusion Criteria**

- a) meeting DSM-5 criteria for substance use disorder aside from tobacco use disorder and mild cannabis use disorder
- b) recent (30 day) illicit drug use (except marijuana), based on self-report and urine drug screen
- c) Past 30-day use of tobacco cessation aids or nicotine/tobacco products other than cigarettes
- d) Past 30-day use of SSRIs, other psychiatric medications, or weight control medications
- e) lifetime diagnosis of severe mental illness (e.g., psychotic or bipolar I disorder)
- f) significant medical or neurological illness based on the medical staff (i.e., physician or nurse practitioner) evaluation including severe hepatic impairment or cirrhosis, insulin dependent diabetes g) actively engaged in smoking cessation treatments or a smoking cessation attempt (or intent to start an attempt in the next 90 days)
- h) interested in quitting smoking immediately (i.e., in the next two months)
- i) Medications which are contraindicated for use with lorcaserin (bromocriptine, cabergoline, dapoxetine, dihydroergotamine, ergoloid mesylates, ergonovine, ergotamine, methylene blue, methylergonovine, nicergoline, pergolide, thiorizadine) or which have a significant interaction with lorcaserin (bupropion, doxorubicin, eliglustat, linezolid, perhexiline, rasagiline, safinamide, selegiline, tamoxifen)
- j) body mass index (BMI) under normal range (BMI < 18 kg/m^2)
- k) history of significant cardiovascular conditions including history of arrhythmias or heart block, heart failure, valvular heart disease, heart attack, stroke, unstable angina
- 1) abnormal electrocardiogram (ECG) results
- m) nursing, pregnant, or anticipating pregnancy
- n) history of suicide attempt or recent suicidal ideation (i.e., Suicidal thoughts (intent or plan) in the last month)
- o) Plans to travel outside of the Albuquerque area during the study period, or inability to commit to entire duration of study (6 weeks of potential availability)

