### V. Data Collection Procedures

In total, participation in this study will take roughly 18 hours over a period of approximately 5 weeks. This includes a screening visit (up to 3 hours), a baseline visit (up to 3 hours), and two follow-up visits (up to 5 hours each). In addition, participants will complete a follow-up medication refill visit (1 hr.) and daily questionnaires online (using Redcap) every day (1-2 minutes per day), and will receive calls twice from staff during each of the medication phases to check in on side effects (up to 15 minutes per call).

Participants will be asked to complete the following procedures:

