# Screening and Baseline Data Collection Visits

Prior to any assessments, we will obtain informed consent from all participants. The in-person screening visit will include both a clinically-oriented screen by a medical staff member (study physician or nurse), and self-report and interview questions, conducted by the research assistant or medical staff member. The staff will administer a urine drug screen (for females, the test will also include a pregnancy screen), and then briefly review and verify information collected over the phone. In all cases in which the pregnancy test shows a positive result, the results of the test will be given to only the participant in a private room. We will also measure expired alveolar carbon monoxide (CO) at the screening visit.

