Additional screening criteria, including symptoms of nicotine and alcohol dependence, and aspects of medical history (see criteria listed above) will be assessed. The Structured Clinical Interview for DSM-V [76] will be used to assess inclusionary and exclusionary diagnoses. The Timeline Follow-Back (TLFB) [77] will be used to assess cigarette, alcohol, and other drug use in the 90 days prior to baseline, and the Fagerström Test of Nicotine Dependence [78] will be used to assess nicotine dependence. Consistent with prior studies [39], motivation for cessation at screening will be measured by asking participants about **intent to quit** in the next 3, 6, and 12 months (intent to quit within 12 months serves as the index of motivation, whereas intent to quit within 3 months will be exclusionary). The urine sample will be used to test for the presence of several drugs (for example, marijuana, heroin, cocaine, methamphetamines, opiates). If a participant tests positive for drugs other than marijuana (or if females screen positive for pregnancy) the participant will be excluded from the study. Additionally, participants will complete a blood draw (up to 20 ml) for a complete blood count (CBC), a basic metabolic panel, and a hepatic function panel. The baseline blood sample will also serve as the sample for DNA analysis. Blood draws will be performed by trained research staff. Participants will also complete an ECG test. ECG results will be evaluated by qualified medical staff. During the medical history any medications that the participant is taking will be checked for interactions with lorcaserin in an established online database such as Epocrates or Lexicomp, and prescribing medical staff will be contacted for dose adjustments, if deemed necessary. The initial consent and eligibility interview session is projected to take up to 3 hours.

If results of the baseline screening/medical assessment indicate that the participant is eligible, they will be scheduled for a return baseline visit. This visit will include a more comprehensive orientation to the study, a questionnaire battery, cognitive tasks, and dispensing of the first set of study pills. Any incidental medical findings during the assessment or subsequent participation in the study will be communicated by the MD or NP directly to the participant.

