To assess lorcaserin's effects on behavioral measures of impulsivity, we will use validated measures of impulsive action (a Continuous Performance Test, CPT), and impulsive choice (the Monetary Choice Questionnaire, MCQ, assessing temporal discounting). The Connors' CPT II task [93] requires participants to attend to a sequence of numbers and press a button for every letter that appears on the screen except the letter 'X'. The task outcomes include number of correct detections, (a measure of attentional capacity), reaction time (processing speed), omission errors (distractibility), and commission errors (a measure of impulsivity and the key outcome for this study). Importantly, preclinical studies have found effects of 5-HT2C drugs on impulsivity when using the 5-choice Serial Reaction Time Task [94, 95], which was originally designed as a rodent analogue of the CPT. The MCQ [96] is a measure of temporal discounting (or impulsive choice). Participants indicate their preferences on each of 27 items that present an immediate and delayed reward (e.g. \$19 today or \$25 in 53 days). From these choices, it is possible to derive a discounting value, k, reflecting the extent to which one discounts future rewards in favor of immediate rewards. A similar Cigarette Discounting Task [103], and a Cigarette Purchase Task [104] will further serve as behavioral indices of drugrelated impulsive choice. Finally, given the additional possibility that 5-HT2C agonists may reduce aspects of reward-based responding generally, a Reward Responsiveness Test [97] will be included. In this task, participants must discern between two similar, briefly presented (i.e. 100ms) stimuli. During each block of 100 trials, participants receive rewards on 40 of the correct trials; however, unbeknownst to participants, the two stimuli are rewarded on different reinforcement ratios, leading to systematic bias in responding. The key outcome is response bias (indexing bias towards rewardbased learning).

Table 1. Study Measures

VISIT	MEASURE/PROCEDURE	TIME (MINS)
Screening	Consent	30
	Urine drug screen	5
	Urine pregnancy test (females)	5
	Blood draw	5
	Expired CO	2
	Intention to quit/treatment status	2
	FTND	1
	TLFB	30
	SCID	60
	The Wechsler Test of Adult Reading (WTAR)	10
	Physical Exam	10

VISIT	MEASURE/PROCEDURE	TIME (MINS)
Medical screen (may occur	Medical History	15
on different day than	EKG	20
screening depending on		
availability)		
Baseline/First Dispensing Visit	Demographics form	5

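### Pregnancy is an exclusion, but the only test expressly scheduled is at screening; neither visit that dispenses study pills names a repeat

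*Combined protocol and SAP*

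**What the plan says.** Exclusion criterion (m) rules out participants who are "nursing, pregnant, or anticipating pregnancy".

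Under Screening and Baseline Data Collection Visits, the test accompanies the urine drug screen at the in-person screening visit: "for females, the test will also include a pregnancy screen". The consequence of a positive result is also given: "or if females screen positive for pregnancy) the participant will be excluded from the study". Table 1 carries the matching row, "Urine pregnancy test (females)", once, in the Screening block, with 5 minutes allotted.

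The first supply is not issued at that visit. If the screening and medical results show eligibility, "they will be scheduled for a return baseline visit", and that later visit includes "dispensing of the first set of study pills". The second supply is issued at the washout visit, where Table 1 has the row "Dispense 2 nd medication".

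The paragraph on medication schedule and safety monitoring sets the sequence: a 7-day supply, a laboratory visit on Day 7, a washout of 7 days or more, then the same sequence with the other pill. It allows slight deviations and, at the physician's discretion, extra days of medication. It also says that the Day 7 visit repeats the medical tests mentioned earlier, without listing them.

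**The concern.** An eligibility test protects participants only if its result still holds when the drug is handed over. Here the exclusion is checked once, before a gap of unstated length, and pills are then issued on two later occasions. Barring those who anticipate pregnancy deals with planned conception. It does not deal with a pregnancy that is unplanned or unrecognised, and the visible eligibility criteria contain no contraception requirement.

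The plan does re-check other things that can change. Cigarette and other substance use since the last visit is asked about again at both the baseline and washout visits, and intention to quit is screened by phone and again in person. No matching re-check of pregnancy is named at either dispensing visit.

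What is at stake is participant safety, not inference. The Benefits section says that participants are not expected to gain directly, so avoidable exposure of someone the protocol means to exclude has no personal benefit to set against it.

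**Working it through.** The protocol gives no figure to reproduce. The check compares visit content with the timeline.

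**Visit content**

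| Visit | Pills issued | Pregnancy test named |
|---|---|---|
| Screening | No | Yes (narrative and Table 1) |
| Baseline/First Dispensing | Yes, first supply | No (narrative or Table 1) |
| Day 7 laboratory visit | No | Not by name; an unlisted repeat of medical tests |
| Washout | Yes, second supply | No |

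Three places bear on whether the Day 7 repeat includes a pregnancy test:
- The follow-up rows of Table 1 do not list one.
- The section on minimising risks gives weight, heart rate/blood pressure and ECG as its examples of the repeated examinations.
- Follow-up Sessions 1 and 2 describes the urine sample as being for riboflavin.

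None of these settles the question, because the first is an incomplete list and the second gives examples only.

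**Timeline**

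Inputs, all nominal, from the medication schedule paragraph: first course 7 days; washout *w* of at least 7 days. Let *s* be the days from screening to first dispensing. The protocol does not state *s*. Set first dispensing at Day 0.

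- Day 7 visit: 0 + 7 = Day 7.
- Second dispensing: 7 + *w*, which is at least 7 + 7 = Day 14.
- Age of the screening test at first dispensing: *s*, unknown.
- Age of the screening test at second dispensing: *s* + 7 + *w*, which is at least *s* + 14 days and so at least 14.
- If Day 7 does include a test, its age at second dispensing is *w*, at least 7 days. It comes after the first supply has been issued, so it cannot cover that release.

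With a test at each dispensing visit, the age of the result at release is 0 days both times, whatever *s* and *w* turn out to be.

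**Exposure**

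Each participant receives one lorcaserin course and one placebo course. A participant who became pregnant after screening would therefore take at most one active course, nominally 7 days.

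**The case against.** The strongest reply is that absence from Table 1 proves little. The table omits procedures that the narrative requires. Breath CO, breath alcohol, weight and heart rate/blood pressure are due at every in-person visit, yet the baseline block lists none of them. The baseline saliva sample has no row. The follow-up blocks leave out the riboflavin urine sample, the ECG and the calendar-based review of substance use. The narrative's own list of each-visit measurements is not exclusive either. A pregnancy test could be done at dispensing without appearing in the table. This stands as a limit on the evidence. But the narrative does not name such a test at either dispensing visit, so staff working from the visible text would have no instruction to do it.

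A second reply is that the Day 7 repeat may include the pregnancy screen, since that was among the tests described earlier and urine is collected at that visit anyway. The reading is fair. It would narrow the gap before the second supply to nominally 7 days or more, and leave the first supply as it was.

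Third, the protocol already lets the investigator withdraw participants for a change in health or for safety. That gives authority to act on a pregnancy, but does not detect one.

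Two stronger readings should be resisted:
- A reader might infer that pills are released with no valid check. The documents do not support this. The screening test does gate the first supply, its age at that point is unknown, and the protocol sets no period for which a result remains valid.
- A reader might also try to date the test from the statement that "participation in this study will take roughly 18 hours over a period of approximately 5 weeks". Taking 35 days from screening to the second laboratory visit makes the screening test 35 − 7 = 28 days old at second dispensing. Taking the six weeks of availability in exclusion (o) makes it 42 − 7 = 35. Neither total is a defined visit interval, so only the lower bounds above are used.

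**Conclusion.** The point holds for the visible text. The one expressly scheduled pregnancy test precedes both releases of study pills, by an unstated interval for the first and by nominally at least 14 days for the second. A pregnancy arising in between could go undetected before dispensing.

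It is minor. The number of participants affected cannot be derived, because the protocol gives neither the proportion of women nor the screening-to-baseline interval. The visible text states no pregnancy-specific risk of lorcaserin, so the argument rests on the protocol's own exclusion. Endpoints, power and analysis are untouched.

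The conclusion assumes that no further precaution sits in the removed consent pages, the attached data and safety monitoring plan or the other attachments. If one does, what remains is a request to show it in the schedule. The 14-day and 7-day figures are nominal, given the flexibility allowed in scheduling.

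**What to change.** 1. In Table 1, add the existing pregnancy-test row to the Baseline/First Dispensing Visit and Washout blocks, with the result read before pills are released.
2. Extend the existing screening exclusion to a positive result at either visit: pills are withheld and the participant is withdrawn.
3. In the medication schedule paragraph, list the tests that the Day 7 repeat includes.

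The cost is two urine dip tests per female participant, 2 × 5 = 10 minutes by the time allotted in Table 1, using a test the site already runs at visits that already take place. The other downside is the rare loss of a participant between periods. The planned maximum-likelihood mixed model uses all available cases, so a usable first-period record need not be lost with her.
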